c Study treatment is to be administered once a week, either at the site or at home by a qualified healthcare professional – Last dose will be given at Week 23

d Complete physical examinations will include skin, nasal cavities, eyes, ears, respiratory, cardiovascular, gastrointestinal, neurological, lymphatic, and musculoskeletal systems. For the dermatological examination the Investigator should evaluate for SSc related skin changes and some specific findings that may indicate vasculitis including, but not limited to: purpura, papules or non-blanching rashes. Nail beds (periungual areas) should be examined for “splinter lesions” and digital tuft for tuft purpura or ischemia. Gynecological and urogenital examinations will not be done in this study unless for cause

e Vital signs, including blood pressure (mmHg), heart rate (beats per minute) and body weight (kg) will be measured at screening, baseline and every subsequent visit. Height (cm) will be measured at screening (Visit 1) only. BMI will be calculated automatically at all visits

- f* All abnormal ECG interpretation will be reviewed and confirmed by a local cardiologist.
- g* Previous echocardiogram may be used if obtained within 6 months of V1 (screening visit).
- h* Hematology: Hemoglobin, hematocrit, red blood cell count, erythrocyte sedimentation rate (ESR), white blood cell count with differential and platelet count. Biochemistry: Fasting glucose, blood urea nitrogen, creatinine, sodium, potassium, chloride, bicarbonate, calcium, phosphorous, total protein, albumin, total bilirubin, alkaline phosphatase, ALT, AST, CPK, hs CRP. Urinalysis (dipstick) to include: specific gravity, pH, glucose, ketones, blood, protein, nitrate, leukocyte esterase, urobilinogen and bilirubin. If any parameter on the dipstick is abnormal, a urine sample should be sent to the central laboratory for testing. If positive for protein and/or red blood cells, microscopic analysis will be performed by the central laboratory
- i* Serology testing includes HIV-1/HIV-2 antibody, hepatitis B surface antigen, hepatitis B surface antibody, hepatitis B core antibody, hepatitis B DNA (reflex to a positive hepatitis B core antibody), hepatitis C antibody and hepatitis C RNA (reflex to a positive hepatitis C antibody)
- j* [REDACTED]

- k* Tuberculosis screen: history and QuantiFERON-TB Gold test. If the result of the initial QuantiFERON-TB Gold test is indeterminate, the test should be repeated one time

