9.3 OTHER ENDPOINTS

9.3.1 Pharmacokinetics and Immunogenicity

9.3.1.1 Sampling time

Samples for PK analysis will be collected pre dose (within 2 hours before each dose administration) during Visits 2, 4, 5, 6 and 7.

Pharmacokinetics samples during Visit 8 will be collected in the morning.

Anti-SAR156597 antibodies (ADA) samples will be collected at approximately the same times as the PK samples. An additional ADA sample will be collected at Visit 1.

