2.1.6 Pharmacokinetic variables

All measurements (scheduled or unscheduled) will be assigned to analysis windows, as defined in [Section 2.5.4](#), in order to provide an assessment of the PK parameter at each time point planned to be collected as per protocol.

C_{trough} , $C_{trough,av,ss}$) and $C_{Follow-Up}$ will be defined as follows:

- C_{trough} : SAR156597 concentration sample within 2h before each administration (Day 1, Week 4, Week 8, Week 12 and Week 24).
- $C_{trough,av,ss}$: SAR156597 average trough concentrations (“ $C_{trough,av,ss}$ ”) will be calculated for each patient as the mean of “ $C_{troughs}$ ” considered at steady state (ss). The occurrence of steady state will be assessed graphically, by plotting “ C_{trough} ” throughout the study visits over all patients.
- $C_{Follow-up}$: SAR156597 concentration sample taken in Week 35, 12 weeks after last injection.

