2.1.8 Biomarker endpoints

All measurements (scheduled or unscheduled) will be assigned to efficacy analysis windows defined in [Section 2.5.4](#), in order to describe all biomarkers (BM) assessments by time points even in case of premature treatment discontinuation.

Peripheral blood samples are planned to be collected for measurement of protein biomarkers at the study Visits 2 (baseline visit), Visit 6 (Week 12), Visit 7 (Week 24-EOT), Visit 8 (Week 35-EOS).

The protein biomarkers include, but are not limited to:

- Cartilage Oligomeric Matrix Protein (COMP) analyzed by Enzyme Linked Immuno Sorbent assay (ELISA) method.
- Chemokine (C-C Motif) Ligand 2 (CCL2) analyzed by ELISA method.
- Chemokine (C-C Motif) Ligand 17 - TARC analyzed by ELISA method.
- Periostin analyzed by ELISA method.
- Eotaxin-3 analyzed by Electrochemiluminescence (ECL).

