2.4.7 Analyses of immunogenicity data

The following summaries will be performed on the ADA population, taking into account all samples regardless of timing in relation to injections:

- ADA results (negative, positive or inconclusive) by time point and by treatment arm.
- Neutralizing status (inconclusive or positive) for positive ADA by time point and by treatment arm.

- ADA titers using descriptive statistics (median, Q1, Q3, minimum and maximum) for positive ADA by time point and by treatment arm.
- Number (%) of patients with pre-existing ADA and number (%) of patients with treatment-emergent ADA positive response by treatment arm.
- Number (%) of patients with persistent/transient/indeterminate treatment-emergent ADA positive response by treatment arm.
- Time to onset of treatment-emergent ADA positive response (in days) using descriptive statistics by treatment arm and also according to peak titer.
- Duration of ADA (in days, only for subjects with at least 2 positive ADA samples) using descriptive statistics by treatment arm.

Correlations between ADA parameters (eg, titers, treatment-emergent ADA positive status, neutralizing status) and PK, safety and/or main efficacy endpoint(s) will be explored (eg, scatter plot) according to the study results.

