2.5.4 Windows for time points

Data analyzed by time point (including efficacy, safety, PK, BM and ADA) will be summarized using the analysis windows below. The analysis windows will be exhaustive so that data recorded at any time point (including unscheduled visits) have the potential to be summarized. These analysis windows will be applicable for all analyses, and they are defined to provide more homogeneous data for time point-specific analyses.

- For efficacy, if multiple valid values of a variable exist within an analysis window, the nearest from the targeted study day will be selected. In case of ties, the worst value will be displayed.
- For PK, BM and ADA, if multiple valid values of a variable exist within an analysis window, the value before the injection will be selected.
- For safety, if multiple valid values of a variable exist within an analysis window, the nearest from the targeted study day will be selected. In case of ties, the last value will be displayed (except for ANCA).
- For ANCA and ANA, if multiple valid values of a variable exist within an analysis window, the nearest from the targeted study day will be selected. In case of ties, the positive value with the highest titer will be displayed.

Table 3 - Analysis windows definition for efficacy and safety

Time point	Targeted study day	Analysis window in study days for efficacy (except CRISS) and safety	Analysis window in study days for CRISS
Baseline	1	Last value before first IMP*	
Week 2	15	2 to 21**	
Week 4	29	2 to 42***	
Week 8	57	43 to 70***	
Week 12	85	71 to 126	71 to 126
Week 24 (EOT)	169	127 to 207	127 to 207
Week 35 (EOS)	246	>207	>207

Note: Study days are calculated from the day of first IMP injection, the day of first IMP injection being Day 1. For randomized but not treated patients, Day 1 is the day of randomization.

*except for ANCA.

**only for vital signs.

***except for FVC, DLco, EQ-5D-5L.

The BM, PK and ADA will be analyzed according to the date of corresponded injection. A time windows superior or inferior to 2 days will be accepted. If the date of the previous injection is unknown, the SAR156597 concentration will not be considered for the analysis.

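### SAP 2.5.4 ties biomarker, PK and ADA samples to an undefined injection date that does not fit Weeks 24 and 35 and conflicts with 2.1.8 and 2.4.7; the Week 24 PK trough is also misdefined

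*SAP*

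**What the plan says.** SAP 2.5.4 opens by saying that efficacy, safety, PK, biomarker and ADA data are all summarised in exhaustive analysis windows. Table 3 then gives study-day windows, but its title and column heads name only efficacy and safety. Below the table comes a rule for the other three data types: "The BM, PK and ADA will be analyzed according to the date of corresponded injection". It continues "A time windows superior or inferior to 2 days will be accepted", without saying what the 2 days are measured from, and ends "If the date of the previous injection is unknown, the SAR156597 concentration will not be considered for the analysis".

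Other sections point elsewhere:

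- SAP 2.1.8 puts biomarker samples in the efficacy windows "in order to describe all biomarkers (BM) assessments by time points even in case of premature treatment discontinuation".
- SAP 2.4.7 summarises ADA "taking into account all samples regardless of timing in relation to injections", and 2.1.7 counts treatment-emergent ADA up to the follow-up visit.
- SAP 2.4.8 models biomarker change from baseline to Week 24.
- SAP 2.1.6 defines C_trough as the concentration "within 2h before each administration (Day 1, Week 4, Week 8, Week 12 and Week 24", and C_Follow-up as the Week 35 sample, 12 weeks after the last injection.

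Protocol 9.3.1.1 likewise calls for pre-dose PK samples "during Visits 2, 4, 5, 6 and 7". Yet note c of the protocol flow chart (1.2) says "Last dose will be given at Week 23". Protocol 10.1.7 allocates kits only up to Week 23, and the Visit 7 procedures in 10.1.8 include no injection.

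**The concern.** At Weeks 4, 8 and 12 a dose follows the sample on the same visit, so an injection-linked window makes sense. At Weeks 24 and 35 there is no such dose, and the SAP does not say which injection those samples correspond to. The tie-break for multiple values in the same section, which picks the pre-injection value, has nothing to refer to there either.

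Two programmers could follow the SAP and produce different tables. Patients who stop treatment are asked to attend the remaining visits (protocol 10.3.4). An injection-linked rule would remove their later samples, turning the biomarker comparison into something close to an on-treatment analysis, against 2.1.8. For ADA, the Week 35 sample is the scheduled post-dose sample least exposed to drug interference in the assay, an issue that protocol 9.3.1.3.2 acknowledges. PK troughs and immunogenicity are secondary objectives.

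**Working it through.** **Inputs.** Study day = 1 + 7 × week, with the first injection on Day 1 (SAP 2.5.1, 2.5.4). Last dose: Week 23 (protocol 1.2). Dosing: every 7 ± 2 days from the initial injection (protocol 8.1.4). Visits: ± 2 days (protocol 1.2, 10.1). Post-baseline sampling: PK and ADA at Weeks 4, 8, 12, 24 and 35; biomarkers at Weeks 12, 24 and 35.

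**The plan's own figure.** Last dose = 1 + 7 × 23 = Day 162. Week 35 = 1 + 7 × 35 = Day 246. (246 − 162)/7 = 84/7 = 12.0 weeks, matching SAP 2.1.6.

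**Gaps from last dose to sample.**

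- Week 24 = Day 169: nominal gap 169 − 162 = 7 days; with both ± 2-day windows, 3 to 11 days.
- Week 35: nominal gap 84 days; range 80 to 88 days.

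**Three readings of the tolerance.** Each visit has 5 possible visit days × 5 possible dose days = 25 on-schedule combinations. These are counts of cases, not probabilities.

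| Reading | Week 24 in window | Week 35 in window |
|---|---|---|
| Within 2 days of an injection | 0 of 25 | 0 of 25 |
| 7 ± 2 days after the previous injection (5 to 9 days) | 19 of 25, including the nominal case | 0 of 25 |
| Within 2 days of the nominal visit day | 25 of 25 | 25 of 25 |

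For the second row, the Week 24 gap is 7 + v − d, where v and d are the visit and dose shifts, each from −2 to 2. |v − d| ≤ 2 in 5 + 8 + 6 = 19 combinations and exceeds 2 in 6.

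**Time points lost.** The first reading loses Weeks 24 and 35: 2 of 3 biomarker time points and 2 of 5 ADA time points. Among ADA samples only Weeks 4, 8 and 12 remain, at most 12 − 4 = 8 weeks apart, so the 16-week separation for a persistent response (SAP 2.1.7) could not be met from scheduled samples. The second reading loses Week 35: 1 of 3 for biomarkers and 1 of 5 for ADA. Week 35 PK has its own definition as C_Follow-up.

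**Early discontinuation.** On the second reading, any sample more than 9 days after the last dose is outside the window. For illustration, with a last dose at Week 10 (Day 71), the Week 12 sample (Day 85) is 14 days later and the Week 24 sample 98 days later. The sample-size section assumes 10% stop treatment, or 0.10 × 94 ≈ 9 patients.

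**Drug interference.** With the half-life of about 15 days given in protocol section 4, Week 35 is 84/15 = 5.6 half-lives after the last dose.

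**Week 24 trough.** A sample within 2 hours before an administration needs an administration. None is scheduled at Visit 7, so the definition fails whichever reading of 2.5.4 is taken.

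**The case against.** A reader might infer that 2.5.4 discards every Week 24 and Week 35 sample, leaving the Week 24 biomarker model with no Week 24 data. The documents do not support that. The section does not say that samples outside the tolerance are dropped. Its only explicit exclusion is a concentration with an unknown previous injection date. That sentence makes a 7 ± 2-day reading plausible for PK, and on it the nominal Week 24 sample stays. The opening of 2.5.4 together with 2.1.6, 2.1.8, 2.4.7 and 2.4.8 shows that the samples are meant to be used.

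The interference argument is also limited. A Week 24 sample 7 days after a dose is at the same nominal interval as the earlier troughs, so the argument applies only to Week 35 and to patients who stopped early. The PK and ADA analyses are descriptive, and biomarkers are exploratory.

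All of this stands, and it limits the point to an ambiguity and a contradiction. It does not remove them. The only reading that keeps every on-schedule sample is anchored on the nominal visit day, and at Weeks 24 and 35 that is not an injection date. Citing 2.1.8 and 2.4.7 as the true intent amounts to saying that 2.5.4 needs correcting.

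**Conclusion.** The point holds as an internal contradiction in the SAP, not as a demonstrated loss of data. On either injection-anchored reading, Week 35 biomarker and ADA samples and later samples from early discontinuers fall outside the window, against 2.1.8, 2.4.7 and the ADA definitions in 2.1.7. Whether Week 24 samples qualify depends on the reading: none on the strictest, the nominal sample and 19 of 25 on-schedule combinations on the other. The Week 24 trough definition is wrong as written on any reading.

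The effect is confined to secondary PK and ADA summaries and exploratory biomarker analyses; the primary mRSS analysis is untouched. The gaps assume that doses and visits stay within their protocol windows, and off-schedule dosing would change individual cases.

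**What to change.** - **SAP 2.5.4:** assign all biomarker and ADA samples to the Table 3 study-day windows regardless of injection date, and extend the table title to cover them. Limit the injection-timing rule to PK troughs, name the reference injection and state what the 2 days are measured from. Align the multiple-value rule, so that biomarker and ADA samples without a same-day dose have a selection rule.
- **SAP 2.1.6:** define the Week 24 trough relative to the previous (last) injection, nominally 7 days, with a stated tolerance. On-schedule gaps run from 3 to 11 days, so a 7 ± 2-day limit would exclude 6 of the 25 on-schedule combinations; the choice should be deliberate. Reconcile this with the Visit 7 pre-dose wording in protocol 9.3.1.1.
- **C_Follow-up:** keep the Week 35 PK sample under this name, report actual time since last injection and identify early discontinuers. In the Week 10 illustration the gap would be 246 − 71 = 175 days (25 weeks), not 12 weeks.

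The cost is a few sentences of SAP text and the matching programming specification. No extra data are needed.

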2.5.5 Unscheduled visits

For all analyses, unscheduled visit measurements may be used to provide a measurement for a time point.

2.5.6 Pooling of centers for statistical analyses

Not applicable.

2.5.7 Statistical technical issues

Not applicable.

3 INTERIM ANALYSIS

As there is no major enrollment issue, no futility analysis is planned.

Early analysis:

The primary analysis of efficacy and safety will be performed on the data collected during the 24-week treatment period. The results of this analysis will not be used to change the conduct of the follow-up in any aspect.

The analysis will be conducted in two steps:

- First step: Main efficacy and safety analyses.
- The first analysis will be conducted when all patients have been randomized and have at least all their data up to Week 24 collected and validated, and will consist in the final analysis of the efficacy endpoints up to Week 24. The safety analysis will be performed on all safety data collected and validated at the time of first analysis. The results of the first analysis will not be used to change the conduct of the ongoing study in any aspect. The 24-week data will not be reanalyzed at the end of the study. Individuals who have access to patients' source documents will remain blinded with regards to the treatment arm of individual patients throughout the study. Treatment arm will not be disclosed on Data Surveillance reports.
- Second step: Final analysis.
- The second analysis will be conducted at the end of the study and will consist in the final analysis of Week 35 efficacy endpoints and final safety analysis.

4 DATABASE LOCK

The database is planned to be locked 28 days after last patient last visit.

There are two database locks planned for this study as follows:

- First database lock (for early analysis of the main efficacy and safety analyses evaluation at Week 24): 4 weeks after last patient last efficacy visit (Visit 7 Week 24).
- Final database lock (for final analysis of efficacy endpoints and final safety analysis at Week 35): 4 weeks after last patient last visit (Visit 8 Week 35).

5 SOFTWARE DOCUMENTATION

All summaries and statistical analyses will be generated using SAS Version 9.0 or higher.

Appendix A Potentially clinically significant abnormalities criteria

CRITERIA for POTENTIALLY CLINICALLY SIGNIFICANT ABNORMALITIES for Phase 2/3 studies (oncology excepted)

Parameter	PCSA	Comments
Clinical Chemistry		
ALT	By distribution analysis: >3 ULN >5 ULN >10 ULN >20 ULN	Enzymes activities must be expressed in ULN, not in IU/L. Concept paper on DILI - FDA draft Guidance Oct 2007. Internal DILI WG Oct 2008. Categories are cumulative. First row is mandatory. Rows following one mentioning zero can be deleted.
AST	By distribution analysis: >3 ULN >5 ULN >10 ULN >20 ULN	Enzymes activities must be expressed in ULN, not in IU/L. Concept paper on DILI - FDA draft Guidance Oct 2007. Internal DILI WG Oct 2008. Categories are cumulative. First row is mandatory. Rows following one mentioning zero can be deleted.
Alkaline Phosphatase	>1.5 ULN	Enzymes activities must be expressed in ULN, not in IU/L. Concept paper on DILI - FDA draft Guidance Oct 2007. Internal DILI WG Oct 2008.
Total Bilirubin	>1.5 ULN >2 ULN	Must be expressed in ULN, not in μ mol/L or mg/L. Categories are cumulative. Concept paper on DILI - FDA draft Guidance Oct 2007. Internal DILI WG Oct 2008.
Conjugated Bilirubin	>35% Total Bilirubin and TBILI>1.5 ULN	Conjugated bilirubin dosed on a case-by-case basis.
ALT and Total Bilirubin	ALT >3 ULN and TBILI >2 ULN	Concept paper on DILI - FDA draft Guidance Oct 2007. Internal DILI WG Oct 2008. To be counted within a same treatment phase, whatever the interval between measurement.

**CRITERIA for POTENTIALLY CLINICALLY SIGNIFICANT ABNORMALITIES
for Phase 2/3 studies (oncology excepted)**

Parameter	PCSA	Comments
CPK	>3 ULN >10 ULN	FDA Feb 2005. Am J Cardiol April 2006. Categories are cumulative. First row is mandatory. Rows following one mentioning zero can be deleted.
CLcr (mL/min) (Estimated creatinine clearance based on the Cokcroft-Gault equation)	<15 (end stage renal disease) ≥15 - <30 (severe decrease in GFR) ≥30 - <60 (moderate decrease in GFR) ≥60 - <90 (mild decrease in GFR) ≥90 (normal GFR)	FDA draft Guidance 2010. Pharmacokinetics in patients with impaired renal function-study design, data analysis, and impact on dosing and labeling.
eGFR (mL/min/1.73m ²) (Estimate of GFR based on an MDRD equation)	<15 (end stage renal disease) ≥15 - <30 (severe decrease in GFR) ≥30 - <60 (moderate decrease in GFR) ≥60 - <90 (mild decrease in GFR) ≥90 (normal GFR)	FDA draft Guidance 2010. Pharmacokinetics in patients with impaired renal function-study design, data analysis, and impact on dosing and labeling.
Creatinine	≥150 µmol/L (Adults) ≥30% change from baseline ≥100% change from baseline	Benichou C., 1994.
Uric Acid		Harrison- Principles of internal Medicine 17 th Ed., 2008.
Hyperuricemia	>408 µmol/L	
Hypouricemia	<120 µmol/L	
Blood Urea Nitrogen	≥17 mmol/L	
Chloride	<80 mmol/L ≥115 mmol/L	
Sodium	≤129 mmol/L ≥160 mmol/L	
Potassium	<3 mmol/L ≥5.5 mmol/L	FDA Feb 2005.
Total Cholesterol	≥7.74 mmol/L	Threshold for therapeutic intervention.
Triglycerides	≥4.6 mmol/L	Threshold for therapeutic intervention.
Lipasemia	≥3 ULN	

**CRITERIA for POTENTIALLY CLINICALLY SIGNIFICANT ABNORMALITIES
for Phase 2/3 studies (oncology excepted)**

Parameter	PCSA	Comments
Amylasemia	≥ 3 ULN	
Glucose		
Hypoglycaemia	≤ 3.9 mmol/L and $< LLN$	ADA May 2005.
Hyperglycaemia	≥ 11.1 mmol/L (unfasted); ≥ 7 mmol/L (fasted)	ADA Jan 2008.
HbA1c	$>8\%$	
Albumin	≤ 25 g/L	
CRP	>2 ULN or >10 mg/L (if ULN not provided)	FDA Sept 2005.
Hematology		
WBC	<3.0 Giga/L (Non-Black); <2.0 Giga/L (Black)	Increase in WBC: not relevant.
	≥ 16.0 Giga/L	To be interpreted only if no differential count available.
Lymphocytes	>4.0 Giga/L	
Neutrophils	<1.5 Giga/L (Non-Black); <1.0 Giga/L (Black)	International Consensus meeting on drug-induced blood cytopenias, 1991.
		FDA criteria.
Monocytes	>0.7 Giga/L	
Basophils	>0.1 Giga/L	
Eosinophils	>0.5 Giga/L or $>ULN$ (if $ULN \geq 0.5$ Giga/L)	Harrison- Principles of internal Medicine 17 th Ed., 2008.
Hemoglobin	≤ 115 g/L (Male); ≤ 95 g/L (Female)	Criteria based upon decrease from baseline are more relevant than based on absolute value. Other categories for decrease from baseline can be used (≥ 30 g/L, ≥ 40 g/L, ≥ 50 g/L).
	≥ 185 g/L (Male); ≥ 165 g/L (Female)	
	Decrease from Baseline ≥ 20 g/L	
Hematocrit	≤ 0.37 v/v (Male) ; ≤ 0.32 v/v (Female)	
	≥ 0.55 v/v (Male) ; ≥ 0.5 v/v (Female)	
RBC	≥ 6 Tera/L	Unless specifically required for particular drug development, the analysis is redundant with that of Hb. Otherwise, consider FDA criteria.
Platelets	<100 Giga/L	International Consensus meeting on drug-induced blood cytopenias, 1991.
	≥ 700 Giga/L	

**CRITERIA for POTENTIALLY CLINICALLY SIGNIFICANT ABNORMALITIES
for Phase 2/3 studies (oncology excepted)**

Parameter	PCSA	Comments
Urinalysis		
pH	≤4.6	
	≥8	
Vital signs		
HR	≤50 bpm and decrease from baseline ≥20 bpm ≥120 bpm and increase from baseline ≥20 bpm	To be applied for all positions (including missing) except STANDING.
SBP	≤95 mmHg and decrease from baseline ≥20mmHg ≥160 mmHg and increase from baseline ≥20 mmHg	To be applied for all positions (including missing) except STANDING.
DBP	≤45 mmHg and decrease from baseline ≥10 mmHg ≥110 mmHg and increase from baseline ≥10 mmHg	To be applied for all positions (including missing) except STANDING.
Orthostatic Hypotension		
Orthostatic SDB	≤20 mmHg	
Orthostatic DBP	≤-10 mmHg	
Weight	≥5% increase from baseline ≥5% decrease from baseline	FDA Feb 2007.
ECG		
Ref.: ICH E14 guidance (2005) and E14 Q&A (2012), and Cardiac Safety Research Consortium White Paper on PR and QRS (Nada et al. Am Heart J. 2013;165(4):489-500)		
HR	<50 bpm ≤50 bpm and decrease from baseline ≥20 bpm <40 bpm <40 bpm and decrease from baseline ≥20 bpm <30 bpm <30 bpm and decrease from baseline ≥20 bpm	Categories are cumulative.
	>90 bpm >90 bpm and increase from baseline ≥20bpm >100 bpm >100 bpm and increase from baseline ≥20bpm >120 bpm >120 bpm and increase from baseline ≥20 bpm	Categories are cumulative.

**CRITERIA for POTENTIALLY CLINICALLY SIGNIFICANT ABNORMALITIES
for Phase 2/3 studies (oncology excepted)**

Parameter	PCSA	Comments
PR	>200 ms >200 ms and increase from baseline $\geq 25\%$ >220 ms >220 ms and increase from baseline $\geq 25\%$ >240 ms >240 ms and increase from baseline $\geq 25\%$	Categories are cumulative.
QRS	>110 ms >110 msec and increase from baseline $\geq 25\%$ >120 ms >120 ms and increase from baseline $\geq 25\%$	Categories are cumulative.
QT	>500 ms	
QTc	Absolute values (ms) >450 ms >480 ms >500 ms	To be applied to any kind of QT correction formula. Absolute values categories are cumulative. QTc >480 ms and $\Delta QTc >60$ ms are the 2 PCSA categories to be identified in individual subjects/patients listings.
	Increase from baseline Increase from baseline $]30-60]$ ms Increase from baseline >60 ms	

